#### *Neuroendocrine prostate cancer (NEPC)*

NEPC develops *de novo* in some patients and in up to 15–20% of patients with metastatic prostate cancer treated with androgen deprivation therapy. In a review of 87 patients with NEPC retrospectively identified at Weill Cornell Medicine (WCM) between 2004 and 2017, 75% of patients with *de novo* NEPC and 92% of patients with treatment related NEPC had liver metastases at the time of diagnosis of NEPC, respectively (Eur J Cancer . 2019 Nov;121:7-18). Dependence on androgen receptor (AR) signaling is lost as tumors progress from a prostate adenocarcinoma to a NEPC histology, typically manifest by downregulation of AR, PSA, and PSMA expression in tumors (Curr Oncol Rep. 2021 Jan 12; 23(2):15). Genomic analyses from patient biopsies combined with preclinical modeling has pointed to loss of tumor suppressors RB1 and TP53 as important genomic events that contribute to NEPC development. Treatment related NEPC is resistant to most therapies and has a poor prognosis with a median survival of less than one year from diagnosis.

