Cabozantinib was not associated with improved PSA response or time to PSA progression. A PSA response, defined as a reduction of 50% or more in PSA level, occurred in 6% of cabozantinib-treated patients and 2% of prednisone-treated patients. The median time to PSA progression was 4.2 and 3 months with cabozantinib and prednisone, respectively (unstratified HR, 0.95; p = 0.639). Because COMET-1 failed to meet its primary endpoint, further development of cabozantinib in the treatment of men with CRPC was halted, and another trial, COMET-2 focused on pain palliation as the primary endpoint for cabozantinib versus mitoxantrone-prednisone in patients with symptomatic bone metastases using patient-reported outcome measures. The study was discontinued after 119 patients were randomized. In this study, cabozantinib did not demonstrate better pain palliation than mitoxantrone-prednisone in heavily pretreated patients with mCRPC and symptomatic bone metastases[35]. A recent analysis of pooled data from patients enrolled on COMET-1 and COMET-2 trials demonstrated that, after adjusting for prognostic factors, cabozantinib use was associated with better overall survival (hazard ratio 0.80, 95% confidence interval 0.67–0.95; p = 0.012)[36].

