## 6 STUDY PROCEDURES

### 6.1 Schedule of Assessments

The study flow chart, including all procedures to be performed during the study, is presented below. Prior to engaging in any study procedure, each patient must sign and date an informed consent form. The following schedule of assessments applies to all subjects; assessments that are more frequent should be obtained if clinically indicated. Cycles are scheduled to be 28 days in length.

If the subject is unable to have a study assessment taken within the defined time window due to an event outside of his or her control (e.g., clinic closure, personal emergency, inclement weather, vacation), the assessment should be performed as close as possible to the required schedule.

Cycle = 28 days	Screening	Cycle 1			Cycle 2	Cycle 3	Cycle 4 +	End of Treatment	Survival Follow-Up
	Day -30 to -1	Day 1	Day 14	Day 21 (+ 3 days)	Day 1 (± 3 days)	Day 1 (± 3 days)	Day 1 (± 3 days)	Post-Treatment	
Informed consent	X								
Medical History 	X								
Physical Exam 	X	X			X	X	X	X	
Vital Signs	X	X	X		X	X	X	X	
Demographics	X								
ECOG Performance Status	X	X			X	X	X	X	
ECG	X								
CBC w. differential and platelet count	X	X			X	X	X	X	
Complete Metabolic Panel 	X	X			X	X	X		
LDH	X	X					X 		
Lipase	X	X 					X 		

 Including cancer history, prior therapy including prior radiotherapy, surgical/pathological reports,

 Including height at baseline and weight at each subsequent visit

 Also include direct bilirubin with known Gilbert's syndrome

	Screening	Cycle 1			Cycle 2	Cycle 3	Cycle 4 +	End of Treatment	Survival Follow-Up
	Day -30 to -1	Day 1	Day 14	Day 21 (+ 3 days)	Day 1 (± 3 days)	Day 1 (± 3 days)	Day 1 (± 3 days)	Post-Treatment	
Cycle = 28 days									
UA and UPCR (24-hr urine, if indicated)	X						X 		
PT/INR and PTT	X								
Thyroid function tests (TSH/FT4 initially. If normal, then TSH thereafter)	X						X 	X	
Testosterone	X						X 	X	
Circulating Immune Activity Sample	X	X 					X 	X	
cfDNA 	X	X 					X 	X	
Tumor assessment (CT/MRI a/p, CT chest bone scan)	X						X 	X 	
PSA sample	X	X					X 	X	
Pre-treatment biopsy 	X								
On-treatment biopsy 				X					
Skeletal-related events 	X	X			X	X	X	X	

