 cfDNA, circulating immune activity, lipase can be collected within 30 days prior to C1D1 or pre-dose C1D1

 When plasma DNA is collected, it should be collected as close to biopsy date as possible, including same day. In the event it is collected on the same day, the specimen should be acquired *prior* to the biopsy procedure.

 Every 12 weeks (± 5 days) until disease progression. For EOT, does not have to be repeated if done within 6 weeks of visit.

 Assess continuously until disease progression

 Every 12 weeks beginning with C4D1 (e.g. C4, C7, C10, etc).

 Collect only on C4D1

 Pre-treatment biopsy can be waived provided that adequate archival material for molecular analyses available from biopsy performed within 3 months of enrollment

 On-treatment biopsy during cycle 1 after 3 weeks of therapy. Biopsy must be performed between day 21 and day 24 on therapy (inclusive). *NB: cabozantinib must be held 5 days before and 5 days after biopsy*

Cycle = 28 days	Screening	Cycle 1			Cycle 2	Cycle 3	Cycle 4 +	End of Treatment	Survival Follow-Up
	Day -30 to -1	Day 1	Day 14	Day 21 (+ 3 days)	Day 1 (± 3 days)	Day 1 (± 3 days)	Day 1 (± 3 days)	Post-Treatment	
Concomitant medications 	X	X			X	X	X	X	
Adverse events 	X	X	X		X	X	X	X	
Health Care Resources 	X	X			X	X	X	X	
Cabozantinib dosing 		X			X	X	X		
Dispense/return of oral study drug and compliance accounting		X			X	X	X	X	
Additional cancer treatment, survival status								X	Subjects will be followed every 12 weeks for 2 years after completion of the study or until death, whichever occurs first

 Document those taken from 30 days prior to treatment through 30 days after the decision to discontinue study treatment

 Document new or worsening events from time of informed consent through 30 days after the last dose of study treatment (related SAEs at any time). Adverse events information will be collected at study visits and may also be collected at any time over the phone or by spontaneous subject report. At study visits where any study treatment is administered, adverse events will be documented pre- and post-dose. Certain AEs and all SAEs that are ongoing 30 days after last dose of study treatment are to be followed until resolution or determination by the investigator that the event is table or irreversible.

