#### **6.9 End of Treatment**

Subjects will return to the study site approximately 30 days after their last dose of cabozantinib to complete end-of-study assessments.

- Physical Examination with vital signs and weight
- ECOG Performance Status
- CBC with differential and platelet count
- CMP (with direct bilirubin with known Gilbert's syndrome)
- Thyroid function tests
- PSA
- Testosterone
- LDH

- Concomitant medications
- Circulating Immune Activity sample
- cfDNA
- Skeletal-related events
- Adverse events
- Return oral study drug
- CT/MRI abdomen/pelvis (if not done within 6 weeks)
- CT chest (if not done within 6 weeks)
- Bone scan (if not done within 6 weeks)

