### **10.1 Response Criteria**

In order to evaluate efficacy, all study-required tumor assessments and PSA measurements must be obtained. Baseline and all post baseline PSA assessments will be used to measure PSA response rate and time to PSA progression based on protocol-specific/modified PCWG3 criteria. Any unscheduled PSA measurement will be included in the periodic assessment of PSA progression.

Radiographic scans (CT, MRI, or bone) will be used to assess best overall response and radiographic progression based on PCWG–modified RECIST criteria for soft-tissue lesions and protocol-specific criteria for bone lesions. Baseline images should be taken during Screening as close as possible to, and never more than 28 days before, Day 1 Week 1. Every effort must be made to ensure the same radiographic method is used before and after treatment at scheduled visits.

Other disease-related signs or symptoms suggestive of progression, including escalating pain not referable to another cause, increased LFT in subjects with baseline liver metastases, increased ascites, declining performance status, and examination findings consistent with disease progression, are valid reasons to consider an unscheduled assessment of tumor status.

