### 10.3 PSA

As long as patient safety is the primary concern, in the absence of other indicators of disease progression, therapy should not be discontinued solely on the basis of a rise in PSA.

For each patient, a waterfall plot will be used to report the percent change in PSA from baseline to 12 weeks (or earlier for those who discontinue therapy) and the maximum decline in PSA that occurs at any point after treatment

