### ***12.3.2 Analysis of Secondary Endpoints***

The median OS will be estimated using Kaplan-Meier methodology. Greenwood's formula will be used to calculate 95% CIs for the Kaplan-Meier estimates. The proportion of men with a meaningful decrease in PSA from baseline (30% and 50% declines will both be used) will be summarized with a binomial point estimate and corresponding 95% binomial CI. Likewise, the proportion of patients with a tumor response (modified RECIST response of CR or PR) will also be estimated with a binomial point estimate and 95% CI.

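### PSA is scheduled only every 12 weeks, so men who stop before day 85 have no scheduled on-treatment value, and the plan leaves open whether they are scored off drug or dropped

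*Combined protocol and SAP*

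**What the plan says.** - **Schedule.** In the section 6.1 table, PSA is marked at Screening, C1D1, Cycle 4 onward and End of Treatment. Footnote 8 sets the Cycle 4 onward frequency: "Every 12 weeks beginning with C4D1 (e.g. C4, C7, C10, etc". The table states that "Cycles are scheduled to be 28 days in length".
- **Visits without PSA.** Section 6.6 lists a blood count and metabolic panel at C2D1 and C3D1, but no PSA.
- **End of Treatment.** Section 6.9 lists PSA, and "Subjects will return to the study site approximately 30 days after their last dose of cabozantinib".
- **What is to be reported.** Section 10.3 plans a waterfall plot of the "percent change in PSA from baseline to 12 weeks (or earlier for those who discontinue therapy) and the maximum decline in PSA" at any point after treatment. Section 12.3.2 estimates, with a binomial 95% CI, "The proportion of men with a meaningful decrease in PSA from baseline (30% and 50% declines will both be used". PSA decline is the first-listed secondary objective (section 1.2.2).
- **Which values count.** Section 10.1 uses all post-baseline PSA values for PSA response and adds: "Any unscheduled PSA measurement will be included in the periodic assessment of PSA progression". Section 6.1 allows more frequent assessments when clinically indicated.
- **Who counts.** Section 12.5.2 assesses response in men who received at least 3 cycles. Section 12.2 replaces, and leaves out of the analysis, certain men who withdraw before 28 days. Section 12.3.2 defines no denominator.

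**The concern.** The schedule does not supply the data that section 10.3 promises. For a man who discontinues early, no scheduled on-drug PSA lies between baseline and stopping. For a man who stays on, the maximum decline is taken over very few values, so an early decline that has partly reversed by week 12 can be missed.

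The analysis rules then pull in different directions. Section 10.3 would use an off-drug sample for early stoppers; section 12.5.2, read literally, would leave them out. Extra draws are permitted and count, so a site that checks PSA monthly gives its patients more chances to register a decline than a site that follows the table. About eight sites are expected (section 4.7). At stake are the size and interpretability of the PSA-decline rates. A PSA that was never drawn cannot be recovered later.

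**Working it through.** No sample size, power or alpha in the plan depends on PSA timing, so there is no stated figure to reproduce. The checks are of the calendar and of the possible size.

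**1. On-treatment values.** With 28-day cycles, day 1 of cycle k is day 1 + 28(k − 1). C4D1 is day 85 and C7D1 is day 169. Scheduled on-treatment post-baseline PSA values are therefore 0 before day 85, 1 from day 85, and 2 by day 169. A draw at every cycle visit (C2 to C7: days 29, 57, 85, 113, 141, 169) would give 6 by day 169. A man who stops between weeks 12 and 24 has one.

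**2. The End of Treatment sample.** Its day is about the last-dose day + 30.

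| Last dose (day) | End of Treatment PSA (about day) |
|---|---|
| 28 | 58 |
| 42 | 72 |
| 56 | 86 |
| 70 | 100 |
| 83 | 113 |

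It is always off drug. For a last dose from about day 55 it is not even earlier than C4D1 (55 + 30 = 85).

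**3. How far a reading can shift (assumed kinetics).** The documents give no PSA kinetics. Assume a true 50% decline followed by exponential regrowth with doubling time D weeks. The decline read g weeks later is 1 − 0.5 × 2^(g/D).

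| Situation | g (weeks) | D = 8 | D = 12 | D = 26 |
|---|---|---|---|---|
| Nadir at week 4, read at week 12 | 8 | 0% | 20.6% | 38.1% |
| Nadir at week 8, read at week 12 | 4 | 29.3% | 37.0% | 44.4% |
| Nadir at last dose, read 30 days later | 30/7 | 27.5% | 36.0% | 43.9% |

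Under these assumptions every reading falls below the 50% threshold and some fall below 30%.

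**4. How many men (rough guide).** The documents give no early-stopping rate. Take time on drug as exponential with the 5.6-month median rPFS quoted in section 12. Twelve weeks is 84/30.4375 = 2.76 months, and 1 − 2^(−2.76/5.6) = 28.9%, or about 8.7 of 30.

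**5. Effect on the rate.** One missed responder is 1/30 = 3.3 points. The exact interval for 2/30 (6.7%) is 0.8 to 22.1%; for 3/30 (10.0%) it is 2.1 to 26.5%. If men with fewer than 3 cycles are dropped instead and none of them responded, the same 2 responders give 2/27 = 7.4%, 2/24 = 8.3% or 2/21 = 9.5%. Off-drug scoring can lower the rate; exclusion can raise it.

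**6. The C2D1 draw.** The on-treatment biopsy is on day 21 to 24, with drug held 5 days before and 5 days after (section 6.1, footnote 11). The hold therefore ends between day 26 (21 + 5) and day 29 (24 + 5). C2D1 is day 29 ± 3 days, so it falls at the end of the hold or shortly after it. A definition of on-treatment values must say how this draw is classed.

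**The case against.** The strongest defence is that the grid looks deliberate. Section 10.6 asks for bone scan, CT and PSA at the same interval, scans are every 12 weeks, and the waterfall plot is at 12 weeks. For a man still on drug at C4D1 the 12-week change is obtained as planned. That stands, but extra draws leave the paired 12-week values intact.

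It is also fair that extra PSA draws are allowed and count, so the gap concerns scheduled draws; and that the endpoint is secondary, with no test. Both limit the weight of the point without removing it.

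A reader might infer more than the documents support:

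- **A downward bias against the 6% PSA response quoted from COMET-1.** The sign is not established. Section 12.5.2 may drop early stoppers, which pushes the other way, and COMET-1's PSA schedule is not given. No comparison with 6% is planned.
- **That 29% of men will lack an on-drug PSA, or far more among those with liver metastases.** rPFS is not time on drug. The first scheduled scan falls at about the same visit as the C4D1 PSA, so men stopped on that scan would normally have a value; stops for toxicity are not counted at all. The 2.1-month median quoted for liver metastases belongs to a control arm that did not receive cabozantinib.
- **A flaw in time to PSA progression.** The background reports that "The median time to PSA progression was 4.2 and 3 months with cabozantinib and prednisone, respectively", which falls between grid points, but section 12 lists no PSA-progression endpoint.
- **A need for a minimum baseline PSA because neuroendocrine disease may enrol.** The protocol describes such disease as "typically manifest by downregulation of AR, PSA, and PSMA expression in tumors", but gives no share of such men in this trial and no size for the effect. An all-men denominator is a legitimate choice.

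**Conclusion.** The point holds as a cheap improvement to a secondary endpoint. It is certain from the documents that no on-treatment post-baseline PSA is scheduled before day 85, that only one is scheduled for a man who stops between weeks 12 and 24, and that the End of Treatment sample is about 30 days off drug. It is equally clear that sections 10.3 and 12.5.2 point to different handling of early stoppers, because nothing says whether 12.5.2 covers PSA.

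The effect can be stated only loosely. Declines can be missed, rather than will be; the direction of bias is open; and ascertainment may depend on site practice. The 29% rests on an exponential curve and on rPFS standing in for time on drug. The regrowth figures rest on assumed doubling times. Each misclassified man moves the rate by 3.3 points in 30, well inside the wide interval such a sample gives.

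**What to change.** 1. Add PSA to the existing blood draws at C2D1, C3D1 and each later cycle visit, and at the visit where treatment is stopped. Keep the 12-week PSA paired with the scans.
2. Define best PSA decline from on-treatment values, state the window, and say how the C2D1 value near the biopsy-related hold is classed. Report the End of Treatment value separately.
3. Reconcile sections 10.3, 12.2, 12.3.2 and 12.5.2 so that all treated men with a baseline PSA stay in the denominator, and say how a man with no on-treatment value is counted.
4. Optionally, tabulate the decline rates by histology beside the all-men rate.

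The cost is one extra assay per cycle on blood already drawn, plus edits to the schedule and section 12. The downside is more early PSA rises to interpret; section 10.3 already says that, absent other signs of progression, a PSA rise alone should not end therapy.

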## 6.2 Screening Visit

### (Day -30 to -1 days before start of treatment)

- Informed Consent
- Demographics
- Medical History
  - Previous therapy
  - Surgical report will include date and type of surgery +/- lymphadenectomy
  - Medication history
  - Radiotherapy report will include modality of therapy with prescribed dose and field and dates of therapy
- Previous systemic (hormonal, chemo, other) therapy – drugs, doses, dates of therapy
- Complete Physical Exam including height and weight
- Vital Signs
- ECOG Performance Status
- CBC with differential and platelet count
- CMP (with direct bilirubin with known Gilbert's syndrome)
- PSA
- Testosterone
- Thyroid function tests (TSH/FT4)
- PT/INR and PTT
- UA and UPCR
- EKG
- Circulating Immune Activity sample (may be collected at screening or pre-dose C1D1)
- cfDNA (may be collected at screening or pre-dose C1D1)
- CT or MRI abdomen/pelvis
- CT chest
- Bone scan
- A biopsy of at least one metastatic site or primary prostate prior to beginning therapy. However, adequate archival metastatic tissue can be used if available in lieu of a biopsy if done when patient had CRPC and within 3 months

## 6.3 Cycle 1, Day 1

- Physical Examination with vital signs and weight
- ECOG Performance Status
- CBC with differential and platelet count
- Lipase (if not obtained during screening)
- CMP (with direct bilirubin with known Gilbert's syndrome)
- PSA
- LDH
- Concomitant medications
- Circulating Immune Activity sample (may be collected at screening or pre-dose C1D1)
- cfDNA (may be collected at screening or pre-dose C1D1)
- Skeletal-related events
- Adverse events
- Dispense oral study drug and compliance accounting

## 6.4 Cycle 1, Day 14

- Vital Signs
- Adverse Events

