**NOTE: Cabozantinib must be held 5 days before and 5 days after biopsy**

#### **6.6 Cycle 2, Day 1 + Cycle 3, Day 1**

- Physical Examination with vital signs and weight
- ECOG Performance Status
- CBC with differential and platelet count
- CMP (with direct bilirubin with known Gilbert's syndrome)
- Concomitant medications
- Skeletal-related events
- Adverse events
- Dispense/return oral study drug and compliance accounting

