### **7.9.2 Cabozantinib**

The most frequent AEs experienced by  $\geq 20\%$  of subjects treated with cabozantinib in descending order of frequency were diarrhea, fatigue, decreased appetite, nausea, weight decreased, PPES, vomiting, constipation, hypertension, dysgeusia, dysphonia, asthenia, and dyspnea. For a full description of the safety profile of cabozantinib, refer to the cabozantinib Investigator's Brochure.

Other medically important but less frequent AEs including arterial thrombotic AEs (e.g. transient ischemic attack [TIA], and myocardial infarction [MI]) and venous thrombotic AEs (e.g. deep vein thrombosis [DVT] and pulmonary embolism), severe hemorrhagic events, proteinuria, wound healing complications, gastrointestinal (GI) perforation, abscesses including intra-abdominal and pelvic abscess, GI and non-GI fistula formation, osteonecrosis, and reversible posterior leukoencephalopathy syndrome (RPLS).

Adverse events associated with laboratory abnormalities experienced by  $\geq 5\%$  of subjects treated with cabozantinib in descending order of frequency were anemia, AST increased, ALT increased, hypothyroidism, hypokalemia, hypomagnesemia, thrombocytopenia, hypocalcemia, hypophosphatemia, lactate dehydrogenase (LDH) increased, lipase increased, neutropenia, hyponatremia, ALP increased, leukopenia, and hyperglycemia.

Adverse events may occur within the first few weeks in the course of treatment with cabozantinib, as cabozantinib is expected to reach steady state exposure at approximately 2 weeks following first dose. Events that generally have an early onset include hypocalcemia, hypokalemia, thrombocytopenia, hypertension, PPES, abdominal pain, mucosal inflammation, constipation, diarrhea, and vomiting.

Adverse events should be managed with supportive care at the earliest signs of toxicity. Dose reductions and treatment interruptions should be considered. Dose reductions are recommended for events that, if persistent, could become serious or intolerable (See Table 7.2).

Cabozantinib should be discontinued for the following AEs: visceral perforation or fistula formation, severe hemorrhage, serious arterial thromboembolic events, nephrotic syndrome, hypertensive emergency, persistent uncontrolled hypertension despite optimal medical management, and RPLS.

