#### **Dehydration**

Dehydration events have been identified with comparable incidence and occurring in a shorter time to onset in the prostate cancer studies than previously experienced with cabozantinib in other tumor types. Extra monitoring/medical management including electrolyte monitoring and/or early dose reduction of patients exhibiting dehydration symptoms and those with risk factors for dehydration is indicated.

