#### **7.9.5 Hemorrhage**

Hemorrhagic events, including serious and sometimes fatal events, have been reported with cabozantinib. Subjects should be monitored for bleeding events with serial complete blood counts and physical examination while on study. The risk of hemorrhage in cabozantinib-treated subjects with brain metastases has not been thoroughly analyzed. Subjects enrolled with treated and stable brain metastases should be monitored with a high index of suspicion if symptoms that could be due to a CNS hemorrhage occur.

Cabozantinib should be held for 5 days before and an additional 5 days after procedures, including biopsies.

Cabozantinib should be discontinued in subjects with serious and life-threatening bleeding events or recent hemoptysis ( $\geq 2.5$  mL of red blood).

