#### **7.9.19 Electrolyte Disorders**

Serum electrolyte disorders including hyponatremia, hypokalemia, hypomagnesemia, and hypophosphatemia have been reported during treatment with cabozantinib, and serum electrolyte levels should be monitored frequently while receiving cabozantinib. Clinically relevant electrolyte disorders should be managed according to the dose modification guidelines as outlined in Section 7.3 or as clinically indicated. Standard clinical practice guidelines should be used for management of electrolyte disorders and may include oral or intravenous replacement.

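### No blood count or metabolic panel is scheduled between C1D1 and C2D1, and C2D1 falls in or just after the biopsy drug hold; adding both at the existing C1D14 visit is a cheap safety improvement

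*Combined protocol and SAP*

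**What the plan says.** The table in Section 6.1 marks CBC and CMP at screening, C1D1, C2D1, C3D1 and each cycle from C4. The C1D14 and C1D21 cells are blank for both tests. The visit lists match: "6.4 Cycle 1, Day 14 - Vital Signs - Adverse Events" is the whole of the Day 14 visit, and Section 6.5 lists only the biopsy, to be done on Days 21 to 24.

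The note to Section 6.5 and footnote 11 of Section 6.1 require a drug interruption: "Cabozantinib must be held 5 days before and 5 days after biopsy".

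The safety text bears on the same period:

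- Section 7.9.2: "cabozantinib is expected to reach steady state exposure at approximately 2 weeks following first dose".
- Section 7.9.2: "Events that generally have an early onset include hypocalcemia, hypokalemia, thrombocytopenia, hypertension, PPES, abdominal pain, mucosal inflammation, constipation, diarrhea, and vomiting".
- Section 7.9.5: "Subjects should be monitored for bleeding events with serial complete blood counts and physical examination while on study".
- Section 7.9.19: "serum electrolyte levels should be monitored frequently while receiving cabozantinib". The same section names magnesium and phosphate disturbances as well as sodium and potassium.

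Section 6.1 also has a general allowance: "assessments that are more frequent should be obtained if clinically indicated".

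**The concern.** Three of the events that Section 7.9.2 lists as early are found mainly in the laboratory: low platelets, low potassium and low calcium. The first two weeks of dosing, up to about steady state, are a natural time to look for them. The schedule brings the patient to clinic on Day 14 but takes no blood, and the next scheduled sample comes when the drug has just been off for about a week and a half.

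What is at stake is patient safety in Cycle 1. A patient without symptoms could have a fall in platelets, potassium or calcium during the first run of dosing that no scheduled test would detect, and the C2D1 result may look better than the on-drug values were. The rPFS analysis, the sample size and the other efficacy endpoints are not affected.

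**Working it through.** The plan states no figure to reproduce, so the check is day arithmetic.

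**Inputs.** Cycles are 28 days, so C2D1 is Day 29; with its window of ±3 days it is Day 26-32 (6.1). The biopsy day *b* is 21, 22, 23 or 24 (6.1 footnote 11; 6.5). The hold is 5 days before and 5 days after. The wording leaves open whether the biopsy day is extra or is the first of the five later days, so both readings are shown.

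- Reading A: off drug from *b* − 5 to *b* + 5 (11 days), dosing resumes on *b* + 6.
- Reading B: off drug from *b* − 5 to *b* + 4 (10 days), dosing resumes on *b* + 5.
- Doses before the hold, both readings: *b* − 6.
- Resumed doses before a sample on day *d*: *d* minus the day of resumption, or 0 if that is negative. This assumes that blood is drawn before that day's dose.

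| Biopsy day | Doses before hold | A: days off | A: resumed doses before a Day 26 / 29 / 32 sample | B: days off | B: resumed doses before a Day 26 / 29 / 32 sample |
|---|---|---|---|---|---|
| 21 | 15 | 16-26 | 0 / 2 / 5 | 16-25 | 0 / 3 / 6 |
| 22 | 16 | 17-27 | 0 / 1 / 4 | 17-26 | 0 / 2 / 5 |
| 23 | 17 | 18-28 | 0 / 0 / 3 | 18-27 | 0 / 1 / 4 |
| 24 | 18 | 19-29 | 0 / 0 / 2 | 19-28 | 0 / 0 / 3 |

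**Results.**

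- No scheduled CBC or CMP covers the 15-18 doses between C1D1 and the hold.
- A Day 29 sample follows 10-11 days off drug and 0-3 resumed doses. Over the whole C2D1 window the range is 0-6 resumed doses.
- There are 4 × 7 = 28 pairs of biopsy day and C2D1 day. Under Reading A, 1 + 2 + 3 + 4 = 10 of them put the sample inside the hold; under Reading B, 0 + 1 + 2 + 3 = 6 do. These are counts of possible pairs, not probabilities.
- The first scheduled sample after more than 6 consecutive doses is C3D1. At Day 57 it follows 27-31 doses since the hold (24-34 over Day 54-60), if there is no other interruption.

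**With the change.** A Day 14 sample follows 13 doses and comes 2-5 days before the hold begins (Day 16-19). The 28-day gap (25-31 with the C2D1 window) becomes 13 days plus 15 days (12-18 with the window).

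**The case against.** The strongest reply is that nothing in the protocol is breached. *Serial* and *frequently* carry no interval, and tests at C1D1, C2D1, C3D1 and every 4 weeks after that are a series. This stands. A reader might infer that Section 6.1 contradicts Sections 7.9.5 and 7.9.19; the documents do not support that.

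A second reply is that Section 6.1 already allows extra tests when indicated, and Section 7.9.15 foresees more laboratory work in patients with hematologic toxicity. Both depend on a prompt. The Day 14 vital signs and adverse event review can supply one for a patient with symptoms, but a silent laboratory change gives none.

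A third reply is that harm is not shown. This also stands. The documents give no event rates for silent early changes at 40 mg and no recovery times, and the early-onset list is not specific to this dose. Entry requires platelets of at least 100,000/mm³, the dose is below the 60 mg approved elsewhere, Section 7.9.15 does not mandate dose changes for hematologic toxicity, and Table 7.3 exempts laboratory abnormalities without clinical relevance from its Grade 3-4 rules. So one cannot say that C2D1 results are uninformative, or that events will be missed.

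Two further inferences are tempting and should not be drawn:

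- The dehydration paragraph under Section 7.9.3 reports that "Dehydration events have been identified with comparable incidence and occurring in a shorter time to onset in the prostate cancer studies". Its request for extra electrolyte checks is triggered by symptoms or risk factors, so it needs no calendar date and is not evidence of a missing one.
- The schedule shows no platelet count or PT/INR just before the on-treatment biopsy. That does not show that the biopsy would go ahead unchecked. Pre-procedure testing can reasonably rest with local practice, and no separate requirement is proposed here.

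**Conclusion.** The point holds as a low-cost safety improvement, not as an error or a contradiction. For up to 30 patients, the 15-18 continuous doses before the biopsy hold have no scheduled laboratory check after Day 1, and the next scheduled sample comes in the hold or within 6 resumed doses of it. That is a weak schedule for the monitoring that Sections 7.9.5 and 7.9.19 ask for, given the early-onset list in Section 7.9.2. Whether any toxicity would in fact be missed cannot be determined from the documents.

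The conclusion rests on these assumptions:

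- The biopsy takes place on Day 21-24 with the full hold, and there is no other dose interruption. A patient with no hold would have 25-31 doses before C2D1, and only the gap after C1D1 would remain.
- Blood is drawn before that day's dose. The protocol does not say so, and dosing is at home; drawing after the dose adds one to each count on a dosing day.
- No half-life or recovery time is assumed.

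**What to change.** - In Sections 6.1 and 6.4, add CBC with platelets and CMP at C1D14. The Day 14 column has no visit window, so state that the draw is to be made before Day 16, the earliest hold day.
- Name magnesium and phosphate as additions where the local CMP does not include them. The protocol does not define the panel, and Section 7.9.19 names both.
- Add a note in Section 6.1 that C2D1 laboratory results fall during or just after the biopsy hold and should be read with that in mind.

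The cost is one routine blood draw per patient, up to 30 in all, at a visit that already takes place, plus a schedule amendment. The statistical section needs no change.
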